9.5.5 Handling of Missing Values

The data required for the statistical analysis of the primary efficacy endpoints are the predictions of responder status (i.e., based on TUV) and the 24-week determination of clinical response using ACR50. Handling of potential missing TUV and/or clinical data and imputation rules are discussed in the SAP.

9.5.6 Interim Analyses

No interim analyses will be performed for this study.

10 DATA HANDLING AND QUALITY ASSURANCE

10.1 Data Recording

Data required according to this protocol is captured in the subject's source documentation and are to be entered onto the electronic CRFs (provided by the sponsor) as soon as possible.

10.1.1 CRF Design

Electronic CRFs (eCRFs) will be used for collecting all data generated during the trial. CRF completion details will be documented in a separate document that will be provided by the sponsor and maintained in the TMF.

10.2 Monitoring

This study will be monitored regularly by a clinical research associate (CRA) from the sponsor or a contract research organization (CRO). Monitoring procedures include one or more visits designed to clarify all prerequisites before the study starts. Interim monitoring visits will take place on a regular basis according to a schedule fixed by mutual agreement. During these visits, the CRA will check for completion of the entries on the CRFs, their compliance with the protocol and with GCP, and will compare the CRF entries with the source data.

All data recorded in the CRF will be captured in the source documentation.

The CRA will verify the correct use of the investigational product. The investigational product will not be supplied to the imaging facility prior to a favorable opinion from the IRB and the regulatory authority and, if appropriate, from the radiation protection authorities. In addition, the CRA will determine whether all AEs and SAEs have been appropriately reported (including adherence to the time periods required for SAEs).

10.3 Data Processing

Study data documentation will be maintained specifying all relevant aspects of data processing for the study (including data validation, cleaning, correcting, releasing). This documentation will be stored in the TMF.

For data coding (e.g., AEs, medication, medical/surgical history), internationally recognized and accepted dictionaries will be used. These and the processes used for coding will be specified in the data management plan.

10.4 Auditing

A member of the sponsor's (or a designated CRO) quality assurance unit may arrange to visit the investigator in order to audit the performance of the study at the study site and the study documents originating there. The auditor(s) will usually be accompanied by a CRA or the study team leader. The investigator will be informed about the outcome of the audit.

In addition, inspections by health authority representatives and IRB(s) are possible at any time. The investigator is to notify the sponsor of any such inspection immediately.

10.5 Archiving

Essential documents shall be archived safely and securely in such a way that ensures that they are readily available upon authorities' request. Patient (hospital) files will be archived according to local regulations and in accordance with the maximum period of time permitted by the hospital, institution, or private practice. Where the archiving procedures do not meet the minimum timelines required by the sponsor, alternative arrangements must be made to ensure the availability of the source documents for the required period.

The investigator/institution notifies the sponsor if the archival arrangements change (e.g., relocation or transfer of ownership).

The investigator site file is not to be destroyed without the sponsor's approval.

The investigator's contract will contain all regulations relevant for the study center.

10.6 Premature Termination of the Study

10.6.1 Termination by the Sponsor

The Sponsor may terminate the study at any time for any of the following reasons:

- 1. Failure to enroll subjects
- 2. Protocol violations
- 3. Inaccurate or incomplete data
- 4. Unsafe or unethical practices
- 5. Questionable safety of the investigational product
- 6. Suspected lack of efficacy of the investigational product
- 7. Administrative decision

10.6.2 Termination by the Investigator

If the Investigator terminates the study prematurely, the Investigator must do the following:

- Return all unused investigational products and related study materials to the Sponsor.
- Provide the IRB(s) and the sponsor with a written statement describing why the study was terminated prematurely. Prompt compliance with this requirement is essential so that the sponsor may comply with its regulatory obligations.

10.6.3 Study as a Whole

The sponsor retains the right to prematurely terminate the study as a whole at any time.

At the discretion of the sponsor, the entire study may be canceled for medical reasons. In addition, the sponsor retains the right to end the study at any time if the study cannot be carried out as agreed upon in the protocol. In case of early termination or suspension of the study, the principal investigator/sponsor will promptly inform the investigator/institutions, regulatory authorities, and IRB of the termination or suspension and the reason for that.

10.6.4 Center

At any time, the study may be terminated at an individual center if:

- The center cannot comply with the requirements of the protocol.
- It is not possible for the center to comply with GCP standards.

10.6.5 Study Participant

Individual subjects may be withdrawn from the study according to the criteria specified in Section 4.3.

11 ETHICAL AND LEGAL ASPECTS

11.1 Ethical and Legal Conduct of the Study

The planning and conduct of this clinical study are subject to national laws. Only when all of the requirements of the appropriate regulatory authority have been fulfilled will the study begin. The study will be conducted in accordance with the ethical principles that have their origin in the Declaration of Helsinki and the ICH-GCP Guidelines of 17 Jan 1997 including Integrated Addendum to ICH E6(R1) as well as the Guideline For Good Clinical Practice E6(R2) of 24 August 2018. At the discretion of the investigator, the entire study may be canceled for medical reasons. In addition, the sponsor retains the right to end the study for medical-scientific or GCP-relevant reasons. In case of premature termination, the investigators, IRB(s) and Regulatory Authorities will be informed by the Study Manager. As required by local law, current safety-relevant information will be provided to the IRB(s) and the regulatory authorities by the sponsor. The sponsor will also inform all investigators about relevant safety events according to the applicable regulations.

11.2 Subject Information and Consent

All relevant information on the study will be summarized in the subject consent form and additionally as required by the investigator's institution in an integrated subject information and consent sheet. A sample informed consent form (ICF) is provided as a document separate to this protocol.

Based on this subject ICF, the investigator will explain all relevant aspects of the study to each subject, before entry into the study (i.e., before examinations and procedures associated with selection for the study are performed).

The investigator will also mention that written approval of the IRB has been obtained. Each subject will have ample time and opportunity to ask questions and will be informed about the right to withdraw from the study at any time without any disadvantage and without having to provide reasons for this decision. Following this informative discussion, the subject will be asked if he/she is willing to sign and personally date a statement of informed consent. Only if the subject voluntarily agrees to sign the ICF and has done so, may he/she enter the study. Additionally, the investigator or his/her designee will personally sign and date the form. The subject will receive a duplicate of the signed and dated form.

The investigator will record in the source documentation the consent process including the time and date of obtaining informed consent. In the event that informed consent is obtained on the date that baseline study procedures are performed, the study record or subject's clinical record must clearly show that informed consent was obtained prior to these procedures.

The ICF and any other written information provided to subjects will be revised whenever important new information becomes available that may be relevant to the subject's consent, or there is an amendment to the protocol which necessitates a change to the content of the subject information and/or the written ICF. The investigator will inform the subject of changes in a

timely manner and will ask the subject to confirm his/her participation in the study by signing the revised ICF. Any revised written ICF and written information must receive the IRB's approval/favorable opinion in advance of use.

11.3 Financing/Financial Disclosure

Each investigator (including principal and/or any subinvestigators; as well as their spouses and dependent children) who is directly involved in the treatment or evaluation of research subjects has to provide a financial disclosure according to all applicable legal requirements. All relevant documentation will be filed in the sponsor trial master file and the investigator site file, as appropriate.

11.4 Publication Policy

The sponsor will be responsible for determining when any trial results should be published. The sponsor will work jointly with the investigator(s) to publish information in a timely manner. The investigator(s) shall not submit any information gleaned under the direct support or sponsorship of the sponsor to journals or professional societies without the prior written approval of the sponsor. A "publication" is meant to include any abstract, letter, manuscript or public announcement in any form or length that contains information gleaned under the direct support or sponsorship of the sponsor.

11.5 Subject Injury

In general, if a subject is injured as a direct result of the investigational product but not due to medical negligence on the part of the principal investigator or study staff, the sponsor will pay for reasonable and necessary medical treatment for the injury, to the extent the expenses are not covered by the subject's medical insurance, a government program, or other responsible third party. If laws or regulations of the locality in which the study is taking place require additional payment of expenses, the sponsor shall comply with such law or regulation. Where applicable, the sponsor has taken specific national insurance.

Appendix 1 Schedule of Events

Evaluation	Visit #1	Visit #2 (Day 0)				Visit #3	Visit 4 (5 ± 1 Week Post-Treatment Change)					
	Screening (Day -30 to -1)	- 00:30 to - 00:01	00:00	00:01 to 00:30	60 to 75 min	After Imaging ^a	Telephone (Day 5 ± 3)	- 00:30 to - 00:01	00:00	00:01 to 00:30	60 to 75 min	After Imaging
Informed consent	X											
Entry criteria	x											
Medical History, RA History, Demography	X											
2010 ACR/EULAR	X											
Vital signs	X	X		X				X		X		
Physical Examination	X											
DAS28	X							X				
CDAI ^b	X							X				
HAQ-DI ^{©b}	X							X				
WPI ^b	X							X				
Clinical laboratory evaluation: chemistry, hematology, UA	Х					X						X
RA panel	X											X
Urine pregnancy test WCBP	X	X						X				
Tc 99m tilmanocept administration			х						X			
Planar Imaging: bilateral hands and wrists					х						х	
Concomitant medications	X	X					X	X				
AE monitoring	X	X	X	X	X	X	X	X	X	X	X	X

^a Initiation of anti-TNFα bDMARD therapy change will occur following Day 0 procedures; ^b May be completed up to 30 days prior to imaging Visit 2 and up to 7 days prior to imaging Visit 4;

Confidential Page 78 of 89

	Visit #5	Visit #6 (12 ± 1 Week Post-Treatment Change)	Visit #8 (24 ± 1 Week Post Treatment Change)
Evaluation	Telephone (5 ± 3 days after Visit 4)		
Informed consent			
Entry criteria			
Medical History, RA History, Demography			
2010 ACR/EULAR			
Vital signs			
Physical Examination			
DAS28 ^b		X	x
CDAI ^b		X	x
HAQ-DI ^{© b}		X	x
WPI ^b		X	x
Clinical laboratory evaluation: chemistry, hematology, UA			
RA panel		X	X
Urine pregnancy test WCBP			
Tc 99m tilmanocept administration			
Planar Imaging: bilateral hands and wrists			
Concomitant medications	X		
AE monitoring	X	X	X

Note: Visits 7 and 9 will not be conducted per this protocol amendment

Confidential Page 79 of 89

Appendix 2 2010 ACR/ EULAR Classification Criteria

Score

Target population (Who should be tested?): Patients who

- 1. Have at least 1 joint with definite clinical synovitis (swelling)*
- 2. With the synovitis not better explained by another disease†

Classification criteria for RA (score-based algorithm: add score of categories A-D; a score of $\geq 6/10$ is needed for classification of a patient as having definite RA) ‡

A.	Joint involvement §	
	1 large joint	0
	2 - 10 large joints	1
	1 - 3 small joints (with or without involvement of large joints) #	2
	4 - 10 small joints (with or without involvement of large joints)	3
	> 10 joints (at least 1 small joint) **	5
B.	Serology (at least 1 test result is needed for classification) ‡‡	
	Negative RF and negative ACPA	0
	Low-positive RF or low-positive ACPA	2
	High-positive RF or high-positive ACPA	3
C.	Acute-phase reactants (at least 1 test result is needed for classification) ‡‡	
	Normal CRP and normal ESR	0
	Abnormal CRP or abnormal ESR	1
D.	Duration of symptoms §§	
	< 6 weeks	0
	≥ 6 weeks	1

^{*} The criteria are aimed at classification of newly presenting patients. In addition, patients with erosive disease typical of rheumatoid arthritis (RA) with a history compatible with prior fulfillment of the 2010 criteria should be classified as having RA. Patients with longstanding disease, including those whose disease is inactive (with or without treatment) who, based on retrospectively available data, have previously fulfilled the 2010 criteria should be classified as having RA.

[†] Differential diagnoses vary among patients with different presentations, but may include conditions such as systemic lupus erythematosus, psoriatic arthritis, and gout. If it is unclear about the relevant differential diagnoses to consider, an expert rheumatologist should be consulted.

 $[\]ddagger$ Although patients with a score of $\le 6/10$ are not classifiable as having RA, their status can be reassessed and the criteria might be fulfilled cumulatively over time.

[§] Joint involvement refers to any swollen or tender joint on examination, which may be confirmed by imaging evidence of synovitis. Distal interphalangeal joints, first carpometacarpal joints, and first metatarsophalangeal

joints are excluded from assessment. Categories of joint distribution are classified according to the location and number of involved joints, with placement into the highest category possible based on the pattern of joint involvement.

[figure not shown]
- "Large joints" refers to shoulders, elbows, hips, knees, and ankles.
- # "Small joints" refers to the metacarpophalangeal joints, proximal interphalangeal joints, second through fifth metatarsophalangeal joints, thumb interphalangeal joints, and wrists.
- ** In this category, at least 1 of the involved joints must be a small joint; the other joints can include any combination of large and additional small joints, as well as other joints not specifically listed elsewhere (e.g., temporomandibular, acromioclavicular, sternoclavicular, etc.).
- $\dagger\dagger$ Negative refers to IU values that are less than or equal to the upper limit of normal (ULN) for the laboratory and assay; low-positive refers to IU values that are higher than the ULN but \leq 3 times the ULN for the laboratory and assay; high-positive refers to IU values that are > 3 times the ULN for the laboratory and assay. Where rheumatoid factor (RF) information is only available as positive or negative, a positive result should be scored as low-positive for RF. ACPA = anti-citrullinated protein antibody.
- ‡‡ Normal/abnormal is determined by local laboratory standards. CRP = C-reactive protein; ESR = erythrocyte sedimentation rate.
- §§ Duration of symptoms refers to patient self-report of the duration of signs or symptoms of synovitis (e.g., pain, swelling, tenderness) of joints that are clinically involved at the time of assessment, regardless of treatment status.

Appendix 3 DAS28 Scale

DISEASE ACTIVITY SCORE IN 28 JOINTS (DAS28)

The DAS28 is a frequent outcome measure used in therapeutic trials and is also used to guide treatment decisions and describe disease activity across populations. It is the basis for several other RA measurement tools, including the EULAR response criteria.

FORM A		LEFT		RIGHT	
		SWOLLEN	TENDER	SWOLLEN	TENDER
Shoulder					
Elbow					
Wrist					
Metacarpophalangeal (MCP)	1				
	2				
	3				
	4				
	5				
Proximal Interphalangeal (PIP)	1				
	2				
	3				
	4				
	5				
Knee					
Subtotal					
TOTAL		SWOLLE	EN .	TENDE	٤

FORM B

Swollen (0–28)

Tender (0–28)

ESR (or CRP)

VAS disease activity (0–100mm)

DAS28=0.56*√(TENDER JOINTS) + 0.28*
√(SWOLLEN JOINTS) + 0.70*LN(ESR/CRP) + 0.014*VAS

By comparing a patient's DAS28 score over multiple time points, you can substantiate his/her improvement or response. The EULAR response criteria are defined as follows:

present das28	DAS28 IMPROVEMENT OVER TIME POINTS							
	>1.2	<0.6						
<3.2	good response	moderate response	no response					
3.2-5.1	moderate response	moderate response	no response					
>5.1	moderate response	no response	no response					

Source: DAS-Score.nl. Available at http://www.das-score.nl/www.das-score.nl/index.html. Accessed February 5, 2009.

HOW TO CALCULATE A DAS28 SCORE

- Perform a swollen and tender joint examination of your patient, noting each affected joint on Form A. When complete, add all of the swollen and tender joints and record the totals in the appropriate boxes on Form B.
- 2. Obtain and record the patient's erythrocyte sedimentation rate (ESR) in mm/h in the appropriate box on Form B. Note: C-reactive protein (CRP) levels may be used as a substitute for an ESR.
- 3. Obtain and record the patient's general health on a Visual Analog Scale (VAS) of 100 mm in the appropriate box on Form B. Note: DAS28 calculations may be performed without a VAS measurement.
- 4. Plug the appropriate values into the formula at the bottom of Form B (many online calculators are available to compute this value including http://www.das-score.nl/www.das-score.nl/dasculators.html).
- 5. A DAS28 score of higher than 5.1 is indicative of high disease activity, whereas a DAS28 below 3.2 indicates low disease activity. A patient is considered to be in remission if they have a DAS28 lower than 2.6.

Courtesy of http://www.iche.edu/newsletter/DAS28.pdf

[figure not shown]

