4.1.1 Inclusion Criteria

Each subject must meet the following criteria to be enrolled in this study.

- 1. The subject has provided written informed consent with HIPAA (Health Information Portability and Accountability Act) authorization before the initiation of any study-related procedures.
- 2. The subject is at least 18 years of age and was ≥ 18 years of age at the time of RA diagnosis.
- 3. The subject is a candidate for initiation of, or change to, a new anti-TNF α bDMARD therapy.
- 4. The subject has RA as determined by the 2010 American College of Rheumatology/European League Against Rheumatism (ACR/EULAR) Classification Criteria (score of $\geq 6/10$).
- 5. The subject has moderate to severe RA as determined by a 28-joint disease activity score (DAS28) of ≥ 3.2 (includes the Erythrocyte Sedimentation Rate [ESR] test and Visual Analog Scale [VAS]).
- 6. Subjects receiving traditional DMARDs must have been on therapy for ≥ 90 days and at a stable dose for ≥ 30 days prior to the first imaging visit (Day 0).
- 7. Subjects receiving bDMARD or janus kinase (JAK) inhibitor therapy must have been at a stable dose > 60 days prior to the first imaging visit (Day 0).
- 8. If the subject is receiving NSAIDS (nonsteroidal anti-inflammatory drug) or oral corticosteroids, the dose has been stable for > 28 days prior to the first imaging visit (Day 0). The corticosteroid dose must be ≤ 10 mg/day of prednisone or an equivalent steroid dose.

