8.3.2 DAS28 Evaluation

Subjects will be evaluated for the DAS28 (Prevoo 1995) at the following timepoints: screening (Day -30 to -1), Visit 4 (5 \pm 1 weeks post-initiation of new anti-TNF α bDMARD), Visit 6 (12 \pm 1 weeks post-initiation of new anti-TNF α bDMARD), and Visit 8 (24 \pm 1 weeks post-

initiation of new anti-TNFα bDMARD). DAS28 evaluations may be completed up to 30 days before imaging Visit 2 and up to 7 days before imaging Visits 4, 6, and 8.

DAS28 is calculated from 4 components: Tender Joint Count (TJC), Swollen Joint Count (SJC), visual analogue scale (VAS) of the subject's global health, and the laboratory parameter erythrocyte sedimentation rate (ESR), such that:

$$DAS28 = 0.56\sqrt{TJC} + 0.28\sqrt{SJC} + 0.7\ln(ESR) + 0.014(VAS)$$

A DAS28 score of higher than 5.1 is indicative of high disease activity whereas a DAS28 below 3.2 indicates low disease activity. A subject with a DAS28 lower than 2.6 is considered to be in remission. For consistent scoring, the following calculator should be utilized: https://qxmd.com/calculate/. See Appendix 3 for details.

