4.1.1.2 Clinical Assessments

ACR Response is derived through a combination of reductions from baseline in swollen or tender joint counts as well as improvement from baseline in at least 3 of the other parameters (patient assessment, physician assessment, pain scale, disability/functionality questionnaire, and acute phase reactant [ESR]). This study will evaluate the following three levels of ACR Response:

• ACR20: An ACR20 indicates that 20% improvement is observed in tender and swollen joint counts as well as 20% improvement in at least 3 of the other 5 criteria.

- ACR50: An ACR50 indicates that 50% improvement is observed in tender and swollen joint counts as well as 50% improvement in at least 3 of the other 5 criteria.
- ACR70: An ACR70 indicates that 70% improvement is observed in tender and swollen joint counts as well as 70% improvement in at least 3 of the other 5 criteria.

Each patient will be classified as a yes or a no for whether they meet each of the above ACR Response Criteria at each of the applicable post-baseline time points. Note that the above criteria are nested, such that if a patient is a yes for ACR70 at a given time point, then the patient is also a yes for ACR50 and ACR20 for that same time point.

A patient will be classified as improved on the CDAI depending on the baseline score as follows:

- If the baseline value is greater than 22, a reduction of more than 12 will be classified as improved. Otherwise, the patient is not improved.
- If the baseline value is between 10 and 22 (inclusive) a decrease of more than 6 will classified as improved. Otherwise, the patient is not improved.
- If the baseline value is less than 10, a decrease of more than 1 will be classified as improved. Otherwise the patient is not improved.

A patient will be classified as improved on the DAS28 with a score change of greater than 1.2.

A decrease of at least 0.22 in the HAQ-DI will be classified as improved. Otherwise, the patient is not improved on the HAQ-DI.

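### Appendix 3 allows CRP for ESR in an unchanged DAS28 formula and allows the VAS to be left out, against Protocol 8.3.2 and inclusion criterion 5; if the form of the score changes between a patient's visits, DAS28 moves with no clinical change

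*Protocol*

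**What the plan says.** Protocol 8.3.2 states: "DAS28 is calculated from 4 components: Tender Joint Count (TJC), Swollen Joint Count (SJC), visual analogue scale (VAS) of the subject's global health", and the fourth input is "the laboratory parameter erythrocyte sedimentation rate (ESR), such that". The formula that follows is 0.56√TJC + 0.28√SJC + 0.7 ln(ESR) + 0.014 VAS. Inclusion criterion 5 (4.1.1) sets DAS28 at 3.2 or more and says that the score "includes the Erythrocyte Sedimentation Rate [ESR] test and Visual Analog Scale [VAS" in its bracketed note. Section 8.3.2 names one online calculator for consistency and refers to Appendix 3 for details.

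Appendix 3 differs. Its Form B field accepts either marker. Its formula line ends "SWOLLEN JOINTS) + 0.70*LN(ESR/CRP) + 0.014*VAS", with the same coefficients. Two notes add the permissions: "Note: C-reactive protein (CRP) levels may be used as a substitute for an ESR" and "Note: DAS28 calculations may be performed without a VAS measurement". It gives no CRP unit, no alternative formula, and no rule to keep one form of the score within a patient. It also says that many online calculators exist and points to a different site from 8.3.2.

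SAP 4.1.1.2 sets the response rule: "A patient will be classified as improved on the DAS28 with a score change of greater than 1.2". The SAP gives no DAS28 derivation, and its missing-data table (2.3) covers only the primary endpoints. The shell for Data Listing 21 shows ESR in mm/hr and a patient global VAS, with no CRP column.

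**The concern.** ESR and CRP are different quantities. Putting either into one log term with one coefficient does not give the same score, and dropping the VAS removes a term that is never negative. Section 8.3.2 and the appendix it cites therefore allow scores on different scales to be compared with the same 1.2-point change rule and the same activity cut-offs ("A DAS28 score of higher than 5.1 is indicative of high disease activity whereas a DAS28 below 3.2 indicates low disease activity").

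Three uses of DAS28 are at stake. It is the disease-activity entry threshold. It is one of the clinical criteria in the Week 12 and Week 24 concordance tables, where sensitivity and specificity for ΔTUV bucketing carry p-values. Its change from baseline enters the Kendall correlations with ΔTUV. A switch from ESR to a numerically lower CRP, or a dropped VAS, gives a false fall. The reverse switch can hide a real one.

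**Working it through.** The plan gives no derived figure to reproduce on this point; the 1.2 line is a definition, read here as a fall. The check is algebra on the 8.3.2 formula with the patient's state held fixed.

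**Inputs from the documents:** the coefficients 0.56, 0.28, 0.7 and 0.014; the lines 1.2, 3.2 and 5.1. **Assumed:** all patient values, since the documents give no paired ESR and CRP data; and that an omitted VAS means the term is simply dropped, since Appendix 3 gives no other formula.

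**Size of the artefact**
- CRP entered for ESR: fall = 0.7 ln(ESR) − 0.7 ln(CRP) = 0.7 ln(ESR/CRP).
- VAS left out: fall = 0.014 × VAS.
- Both: the sum of the two.

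**When it exceeds 1.2 by itself**
- Substitution only: ESR/CRP > exp(1.2/0.7) = 5.55.
- Omission only: VAS > 1.2/0.014 = 85.7 mm.
- Both: ESR/CRP > exp[(1.2 − 0.014 VAS)/0.7], which is 3.05 at VAS 30, 2.04 at VAS 50 and 1.37 at VAS 70.

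**Substitution only, over a range of assumed values**

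| ESR | CRP | Fall | Over 1.2? |
|---|---|---|---|
| 20 | 5 | 0.97 | no |
| 30 | 5 | 1.25 | yes |
| 30 | 10 | 0.77 | no |
| 40 | 5 | 1.46 | yes |
| 40 | 20 | 0.49 | no |
| 40 | 40 | 0.00 | no |
| 60 | 10 | 1.25 | yes |

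A tenfold difference in the CRP unit adds 0.7 ln(10) = 1.61, and Appendix 3 names no unit.

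**Worked patient, unchanged between visits:** TJC 6, SJC 4, ESR 30, VAS 50.
- 8.3.2 formula: 1.37 + 0.56 + 2.38 + 0.70 = 5.01.
- CRP 5 entered for ESR: 3.76, a fall of 1.25, counted as improved.
- CRP 10 entered for ESR: 4.24, a fall of 0.77, not counted.
- CRP 10 and no VAS: 3.54, a fall of 1.47, counted.

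**Entry:** TJC 2, SJC 2, ESR 20, VAS 30 gives 3.70, above 3.2. With CRP 5 in the ESR slot the same patient scores 2.73, below it.

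**After alignment:** with the same marker, unit and VAS item at every visit, the artefact is zero for an unchanged patient.

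**The case against.** The best reply is that the trial-specific text already fixes one form of the score. Section 8.3.2 gives four components with ln(ESR) and one calculator; criterion 5 names ESR and VAS; Listing 21 shows only those inputs; and Protocol 3.2 requires strict adherence. Appendix 3 is a reproduced outside leaflet whose main steps still record ESR and a VAS. ESR and CRP come from one panel at screening and Visits 4, 6 and 8 (8.3.5.4), so nothing in the documents describes a visit with CRP but no ESR. A site enrolling on a CRP score would not be applying criterion 5 as worded.

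Much of this stands. It makes substitution less likely, and it means no error rate can be estimated. It does not remove the permission: 8.3.2 itself refers sites to Appendix 3, a listing shell is not a derivation rule, and the two sections point to different calculators.

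The reply is also right about scale. A single substitution at ESR 30 crosses the line at CRP 5 but not at CRP 10; omission alone needs a VAS near the top of the scale; and the larger falls need two departures at once.

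A reader might infer that unchanged patients will commonly be scored as improved. The documents do not support that: it needs a switch between visits, and the values are assumed. A reader might also infer that the moderate/severe subgroup is graded on mixed scales. Protocol 9.5.2 and SAP 2.2.1 name no instrument for that subgroup, and CDAI has activity categories too, so this holds only if DAS28 defines it.

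**Conclusion.** The contradiction between Appendix 3 and 8.3.2 with criterion 5 is plain, and the plan's own formula shows that it can produce a wrong DAS28 classification. By itself the artefact crosses 1.2 at an ESR/CRP ratio above 5.55, at an omitted VAS above 85.7 mm, or at a ratio above about 2.04 when both change at VAS 50. These thresholds follow from the formula, given that an omitted VAS term is simply dropped. Whether patients reach them, and how often, is unknown.

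Two mechanisms should be kept apart. A false change needs different forms of the score at a patient's baseline and follow-up. A site that uses CRP throughout creates no switching artefact, but its entry scores against 3.2 and its DAS28 values are not comparable with those of ESR sites.

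The reach is limited to DAS28 eligibility scoring and the secondary DAS28 concordance and Kendall analyses. It would be wrong to infer a threat to the main result: the co-primary endpoints and the key secondary NPV use Week 24 ACR50, which is not derived from DAS28, and no DAS28 analysis is in the formal testing sequence. This should be corrected, but the study's conclusion does not turn on it.

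**What to change.** 1. Reconcile Appendix 3 with 8.3.2 and criterion 5: remove the two notes, the CRP option in the Form B field, and CRP from the formula line. Point both sections to the same calculator.
2. Name one VAS item. Section 8.3.2 uses the patient's global health, while 8.3.5.2 says that the pain VAS feeds DAS28. Fixing the marker without fixing this leaves a second ambiguity in the same score.
3. State in the SAP that DAS28 is recomputed centrally at every visit from the recorded TJC, SJC, ESR and VAS by the 8.3.2 formula, and is set to missing if any component is missing. The site's total is not used.

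The cost is a short wording change in the protocol and one derivation in the analysis dataset; the components are already planned for Listing 21. The downside is that a few secondary DAS28 values become missing instead of being filled by scores that cannot be compared.
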